We will develop separate mixed-effects general linear models for each of the continuous outcomes. From the anticipated sample size (n=40) the study has 86% power to detect a 10% main effect of each treatment for each outcome, our anticipated effect size given preliminary studies. When using count data the study has 94% power to detect a 10% decrease in the rate of outcomes (coughing, wheezing, etc.), our anticipated change in the rate. Using the dichotomized version of some outcomes, this study has 80% power to detect an odds ratio of 1.32 with a two sided $\alpha=0.05$ (n=40). Therefore, we have more than sufficient numbers of participants in each comparison group.

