7.4 Measures of Treatment Compliance

Parents of subjects will be asked to bring all used and unused Study Drug containers to each study visit. Albuterol use can be documented via changes in the counter.

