8.1.3 Interim Visits

Enrolled subjects will return at 6 weeks as detailed below.

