15.1 Analysis of Physiologic Effects (Lung Function)

The primary goal of the current study is to determine the effects of Aerospan on lung function in children with small airway obstruction. Participants recruited into this randomized parallel group study will be randomly assigned to either receive (1) 80 mcg of Aerospan twice a day or (2) 160 mcg of Aerospan twice a day, during the six-week study period. Outcomes will be measured at baseline and at six-week follow-up as described above.

First we will start with straightforward tests for differences among the two groups to test if our randomization scheme was successful. Analysis of Variance (ANOVA) techniques will be used to test for difference among continuous variables, while Kruskal-Wallis, Fischer's Exact Tests and Wilcoxon methods will be used to test for differences among categorical variables.

The primary endpoint will be changes in outcomes, over time, from baseline to six-week follow-up. The change in scores from baseline to six-week follow-up will initially be compared using paired t-tests and Chi-squared tests for trend. Repeated measurements will be analyzed using generalized linear mixed-effects regression modeling (GLMM) techniques. For continuous outcomes (e.g., FEV1, FEF 25-75%, Fres, X5, AX, R5-R20.) the identity link function and normal distribution will be used. For count data (e.g., use of Beta-agonists, episodes of

coughing, episodes of wheezing, etc.) the log link function and the Poisson distribution will be used. If we dichotomize outcomes (e.g., a Beta-agonist was used, coughing occurred, etc.) the logit link function and Bernoulli distribution will be used. Statistical analyses will be performed using SAS® Version 9.3 (SAS Institute Inc., Cary, NC).

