15.2 Sample Size

Based on our preliminary studies, we anticipate that 10% of all potential participants will not be eligible and/or willing to participant; and that 10% of the eligible/willing participants will be lost to follow-up. Therefore, we will recruit a total of n=50 individuals for the current study. This is a feasible sample size for the research team to recruit and enroll in the current study. Power calculations were based on the anticipated total sample size (n=40) that will be available for complete analysis.

We will develop separate mixed-effects general linear models for each of the continuous outcomes. From the anticipated sample size (n=40) the study has 86% power to detect a 10% main effect of each treatment for each outcome, our anticipated effect size given preliminary studies. When using count data the study has 94% power to detect a 10% decrease in the rate of outcomes (coughing, wheezing, etc.), our anticipated change in the rate. Using the dichotomized version of some outcomes, this study has 80% power to detect on odds ratio of 1.32 with a two sided $\alpha=0.05$ (n=40). Therefore, we have more than sufficient numbers of participants in each comparison group.

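### The stated 80% power for an odds ratio of 1.32 with 40 subjects is wrong at any event rate: with one binary outcome per subject it is at most about 7%

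*Combined protocol and SAP*

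**What the plan says.** Section 15.2 (Sample Size) gives three power figures: 86% for continuous outcomes, 94% for counts, and one for dichotomised outcomes, where "this study has 80% power to detect on odds ratio of 1.32 with a two sided" alpha of 0.05 (n=40). The synopsis row on the rationale for the number of subjects says the same: "this study has 80% power to detect an odds ratio of 1.32". The sample size behind the figure is explicit: "Power calculations were based on the anticipated total sample size (n=40) that will be available for complete analysis". Section 7.2 randomises subjects equally to the two doses, which gives 20 per dose. Both places conclude: "Therefore, we have more than sufficient numbers of participants in each comparison group".

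Section 15.1 says that a logit link and Bernoulli distribution will apply if outcomes are dichotomised, with use of a beta-agonist and occurrence of coughing as examples. On timing it says: "Outcomes will be measured at baseline and at six-week follow-up as described above". On the model: "Repeated measurements will be analyzed using generalized linear mixed-effects regression modeling (GLMM) techniques". No control event rate, number of binary observations per subject or within-subject correlation is given.

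**The concern.** An odds ratio of 1.32 is a small effect on a binary outcome. Near a 50% event rate it is a difference of about 7 percentage points, which 20 subjects per group cannot detect with useful power.

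The figure is one of three offered in support of the conclusion that the sample is ample. A reader who trusts it could take a null result on a dichotomised outcome as evidence against an odds ratio of 1.32, although the study had very little chance of detecting one.

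**Working it through.** **Inputs from the documents.** Odds ratio 1.32, two-sided alpha 0.05, stated power 80%, 40 analysable subjects in total (section 15.2); equal allocation (section 7.2), so n = 20 per dose.

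**Assumed input.** The control event rate p1 is not given, so it was scanned from 0.05 to 0.95 and the most favourable value used.

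**Attempt to reproduce 80%.** The rate in the other arm is p2 = 1.32·p1 / (1 − p1 + 1.32·p1). The large-sample two-proportion test has

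power = Φ[(d − 1.96·s0)/s1] + Φ[(−d − 1.96·s0)/s1],

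where d = p2 − p1, s0 = √(2·p̄(1 − p̄)/n), s1 = √([p1(1 − p1) + p2(1 − p2)]/n) and p̄ = (p1 + p2)/2.

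Power is highest at p1 = 0.465, p2 = 0.534:
- d = 0.0693, s0 = 0.1581, s1 = 0.1577.
- First term: (0.0693 − 0.3099)/0.1577 = −1.525, Φ = 0.0636.
- Second term: (−0.0693 − 0.3099)/0.1577 = −2.404, Φ = 0.0081.
- Power = 0.072.

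Over the whole scan, power runs from 5.4% to 7.2%. Enumerating all outcomes with 20 per arm gives at most 7.3% for the chi-squared test and at most 3.8% for Fisher's exact test. The stated 80% is not reproduced.

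**Sample size for 80%.** n per arm = [1.96·√(2·p̄(1 − p̄)) + 0.8416·√(p1(1 − p1) + p2(1 − p2))]² / d². At p1 = 0.465 this is (1.3859 + 0.5937)² / 0.0693² ≈ 816.1, so 817 per arm, or 1,634 in total. At p1 = 0.3, 0.2 and 0.1 it is 923, 1,178 and 2,034 per arm.

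**More generous readings**

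| Reading | Highest power |
|---|---|
| 25 per arm (all 50 subjects) | 7.7% |
| 40 per arm, or two independent observations per subject | 9.4% |
| One-sided test, 20 per arm | 11.3% |
| Paired (McNemar) test, all 40 pairs discordant | 12% exact, 14% normal |
| Odds ratio per SD of a covariate, n = 40 | 14.0% |
| Baseline adjustment, assumed correlation 0.9 | about 17% |

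**Daily observations.** Six weeks of daily yes/no records would give 42 per subject, or 20 × 42 = 840 per arm. If all were independent, power would be at most 81% (at p1 = 0.465), and 44%, 66% and 76% at p1 = 0.1, 0.2 and 0.3. Correlation within a subject divides the 840 by the design effect 1 + 41·ICC. For assumed ICC values:
- 0.02: effective n = 840/1.82 = 462 per arm, power at most 56%.
- 0.05: 840/3.05 = 275, at most 37%.
- 0.10: 840/5.10 = 165, at most 24%.

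However many records are taken, effective n per arm cannot exceed 20/ICC. Reaching 817 therefore needs an ICC no greater than 20/817 = 0.0245.

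**The case against.** The best defence is that the plan uses mixed models on repeated measurements, so a calculation with one outcome per subject does not describe the planned analysis. Part of this stands. A reader might infer that about 7% is a ceiling on whatever model is fitted. It is not: it applies to one binary outcome per subject, and two-occasion or baseline-adjusted readings reach roughly 9% to 17%. None comes near 80%.

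The sponsor may have assumed independent daily records, since that route gives about 80%. The cause of the error is therefore not established, and it need not be an arithmetic slip. But the supplied text does not describe such a record. Outcomes are taken at baseline and week 6. After baseline there is one return: "Enrolled subjects will return at 6 weeks as detailed below". For rescue use, "Albuterol use can be documented via changes in the counter", which yields a total and not daily yes/no data. The data list in section 16.1 names no diary. The schedule in Appendix 1 and the study manual are not in the supplied text, and section 4.3 does plan to track how often albuterol is used, so a diary cannot be ruled out altogether. Even with one, 80% would require near-independence within a subject, which sits badly with choosing a mixed model.

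It is also fair to say that the harm is limited. The dichotomised analyses are conditional, section 15.2 also rests N on feasibility, and section 15 promises a detailed SAP.

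**Conclusion.** The 80% figure is wrong as written, in section 15.2 and in the synopsis. For a between-dose comparison with one binary outcome per subject and 20 per dose, power for an odds ratio of 1.32 is at most about 7% at any event rate, and the analysable sample is about one fortieth of what 80% would need (40 against 1,634). This rests on the stated total of 40 and equal allocation. It does not depend on the missing event rate, because the most favourable rate was used.

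A reader might go on to infer that the 86% and 94% figures are also wrong, or that the lung-function comparison is underpowered. The documents do not support that. The SD, event rate, dispersion, unit of the 10% and contrast behind those two figures are not stated, so they can be neither confirmed nor refuted. The dichotomised outcomes are not primary, and this error does not touch the lung-function analysis.

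**What to change.** Keep N=50 on its stated feasibility grounds. In section 15.2 and the synopsis:

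1. Delete the statement of 80% power for an odds ratio of 1.32, or replace it with: *With about 20 subjects per dose, the study is not powered for dichotomised outcomes; power for an odds ratio of 1.32 is below 10% in a simple between-dose comparison, and these analyses are exploratory.*
2. Reword the closing adequacy sentence so that it does not cover dichotomised outcomes.

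It would be tempting to substitute a detectable odds ratio. At control rates of 0.1 to 0.5 and 20 per dose, 80% power needs about 6 to 9 (large-sample test) or 8 to 11 (Fisher). That should not go in. Those values hold only if events rise from the control rate, whereas the plan expects improvement with dose and powers its counts for a decrease. Even a fall to zero events gives power of only 30% (large-sample) or 4% (Fisher) from a rate of 0.1, 56% or 37% from 0.2, and 78% or 76% from 0.3. From 0.4, the inverse odds ratio needed is about 15 or 20.

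Stating the inputs behind the 86% and 94% figures would be a useful clarification. It is optional and not part of the demonstrated error.

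The cost is rewording one paragraph in two places, with a less favourable power statement. No patients, endpoints or analyses change.

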16 DATA COLLECTION, RETENTION AND MONITORING

16.1 Data collection

Data that will be collected during the study include: enrollment and randomization information, spirometry/IOS data, other subject data collected during the study visit, and asthma controls scores. This data will be kept in a secure, locked filing cabinet in the pediatric pulmonary clinic office.

An electronic database of data will be created using Microsoft Excel. This database will be encrypted, password protected, and stored exclusively on a password protected computer in the pediatric pulmonary clinic.

16.2 Availability and Retention of Investigational Records

The Investigator must make study data accessible to the IRB upon request. A file for each subject must be maintained that includes the signed Informed Consent, HIPAA Authorization and copies of all source documentation related to that subject. The Investigator must ensure the reliability and availability of source documents from which the information on the CRF was derived. All study documents (subject files, signed informed consent forms, copies of CRFs, Study File Notebook, etc.) must be kept secured for a period of three years.

17 ADMINISTRATIVE, ETHICAL, REGULATORY CONSIDERATIONS

The study will be conducted according to the Declaration of Helsinki, Protection of Human Volunteers (21 CFR 50), Institutional Review Boards (21 CFR 56), and Obligations of Clinical Investigators (21 CFR 312).

To maintain confidentiality, all lung function data, evaluation forms, reports and other records will be identified by a coded number and initials only. All study records will be kept in a locked file cabinet and code sheets linking a subject's name to a subject identification number will be stored separately in another locked file cabinet. Clinical information will not be released without written permission of the subject. The Investigator must also comply with all applicable privacy regulations (e.g., Health Insurance Portability and Accountability Act of 1996, EU Data Protection Directive 95/46/EC).

17.1.1 Protocol Amendments

Any amendment to the protocol will be written by the Study Principal Investigators.

A protocol amendment intended to eliminate an apparent immediate hazard to subjects may be implemented immediately, provided the IRBs are notified within five working days.

17.1.2 Institutional Review Boards and Independent Ethics Committees

The protocol and consent form will be reviewed and approved by the IRB. Serious adverse experiences regardless of causality will be reported to the IRB in accordance with the standard operating procedures and policies of the IRB, and the Investigator will keep the IRB informed as to the progress of the study. The Investigator will obtain a list of IRB members or other assurance of compliance with regulations.

Any documents that the IRB may need to fulfill its responsibilities (such as protocol, protocol amendments, Investigator's Brochure, consent forms, information concerning subject recruitment, payment or compensation procedures, or other pertinent information) will be submitted to the IRB. The IRBs written unconditional approval of the study protocol and the informed consent form will be in the possession of the Investigator before the study is initiated.

Protocol and/or informed consent modifications or changes may not be initiated without prior written IRB approval except when necessary to eliminate immediate hazards to the subjects or when the change(s) involves only logistical or administrative aspects of the study. Such modifications will be submitted to the IRB/IEC and written verification that the modification was submitted and subsequently approved should be obtained.

The IRB must be informed of revisions to other documents originally submitted for review; serious and/or unexpected adverse experiences occurring during the study in accordance with the standard operating procedures and policies of the IRB; new information that may affect

adversely the safety of the subjects of the conduct of the study; an annual update and/or request for re-approval; and when the study has been completed.

17.1.3 Informed Consent Form

Informed consent will be obtained in accordance with the Declaration of Helsinki, ICH GCP, US Code of Federal Regulations for Protection of Human Subjects (21 CFR 50.25[a,b], CFR 50.27, and CFR Part 56, Subpart A), the Health Insurance Portability and Accountability Act (HIPAA, if applicable), and local regulations.

The Investigator will prepare the informed consent form and HIPAA authorization and provide the documents to the IRB. The consent form generated by the Investigator must be approved by the IRB/IEC. The written consent document will embody the elements of informed consent as described in the International Conference on Harmonization and will also comply with local regulations.

A properly executed, written, informed consent and HIPA authorization will be obtained from the legal guardian of each subject prior to entering the subject into the trial. Information should be given in both oral and written form and subjects' legal representatives must be given ample opportunity to inquire about details of the study. A copy of the signed consent form will be given to the legal representative of the subject and the original will be maintained with the subject's records.

